4.3.2. Previous Human Experience SEL-212, SEL-037 alone and SEL-110 alone

4.3.2.1. SEL-037

To date there has been one completed clinical study (Phase I Study SEL-037/101) in humans for SEL-037 under IND 126034. Doses of 0.1, 0.2, 0.4, 0.8 and 1.2 mg/kg SEL-037 administered as single IV infusions to otherwise healthy patients with screening serum uric acid > 6 mg/dL demonstrated no evidence of safety signals as no SAEs or clinically significant treatment-emergent adverse events (TEAEs). SEL-037 demonstrated potent dose-dependent reductions in serum uric acid levels that were below quantification limits from Study Day 2 for all subjects (N=22). The duration of the PD effect was durable to Day 7 for all except 1 subject and to Day 30 in 1 subject. Duration appeared to be subject-dependent, not dose-dependent. The presence of ADA generally correlated with enhanced clearance of SEL-037 and diminished pharmacodynamic activity of SEL-037 at Study Day 14 in 3 subjects (0.1 mg/kg), 2 subjects (0.2 mg/kg), 3 subjects (0.4 mg/kg), and 2 subjects (0.8 mg/kg). At Study Day 30, two subjects with very low anti-uricase antibodies had serum uric acid concentrations below 1 mg/kg. The clinical study report was submitted to IND 126034.

A second Phase I clinical study (SEL-212/101) in humans for SEL-212 (the combination of SEL-110 and SEL-037) under IND 124184 is complete. SEL-212 in this clinical study was tested as a single dose where increasing amounts of SEL-110 were combined with SEL-037 at a fixed dose

level. In this study there were 4 cohorts of SEL-110 alone, 6 cohorts of the combination SEL-212 (SEL-110 with SEL-037), and one cohort of SEL-037 alone. In the cohort of subjects who received SEL-037 alone (0.4 mg/kg), one serious adverse event (SAE) of non-study drug-related atrial fibrillation was reported. In addition, among the 5 subjects who received 0.4 mg/kg SEL-037, the pharmacodynamic activity of SEL-037 was demonstrated by rapid reduction in serum uric acid levels (Figure 1). Data for this clinical study has been submitted to the FDA under IND 124184.

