SEL-212 demonstrated pharmacodynamic activity in reducing serum uric acid levels rapidly at the SEL-037 dose tested (0.4 mg/kg) and reducing or preventing the formation of anti-uricase antibodies in a dose dependent fashion. The uric acid level of all subjects treated with SEL-212 dropped to below 0.1 mg/dL within 24 hours after infusion. SEL-110 appeared to inhibit the formation of anti-uricase antibodies in a dose-dependent manner correlating with more sustained control of uric acid levels (Figure 1). Evaluation of anti-uricase, anti-PEG, and anti-pegsiticase antibodies showed that anti-uricase antibodies were the most sensitive measure of ADAs in the Phase 1 study, corresponding with decreased pharmacodynamic activity of SEL-037 as evidenced by increased serum uric acid levels.

Figure 1: Pharmacodynamic Activity of SEL-212 and Components (SEL-037 and SEL-110)

Pharmacokinetic assessments of concentrations of SEL-110 in whole blood were performed on samples collected from cohorts who received SEL-110 alone and in combination with SEL-037. Results are summarized in Table 7 for cohorts of patients who received SEL-110 doses above ≥ 0.1 mg/kg (ie, suggested minimum therapeutic dose) and showed dose-dependent responses to SEL-110 with potential influence by co-administration with SEL-037. Importantly, the mean and median values for systemic exposure (AUC) of SEL-110 at doses of 0.1 mg/kg and 0.3 mg/kg (Table 7) examined in conjunction with the results of analyses depicted in Figure 2 and Figure 3 suggest that a dose of 0.15 mg/kg SEL-110 will result in systemic exposure substantially below the exposure determined by the recent nonclinical analyses for the NOAEL in rats (Section 4.3.1.2).

Table 7. Summary of SEL-110 Whole Blood PK Parameters

Parameter	Statistic	Cohort 3	Cohort 4	Cohort 5	Cohort 6	Cohort 7
		0.1 mg/kg SEL-110 (alone)	0.1 mg/kg SEL-110 + 0.4 mg/kg SEL-037	0.3 mg/kg SEL-110 (alone)	0.3 mg/kg SEL-110 + 0.4 mg/kg SEL-037	0.5 mg/kg SEL-110 (alone)
C _{max} (ng/mL)	N	4	5	5	5	4
	Mean (SD)	558.5 (181.92)	631.0 (177.87)	1173.8 (326.81)	2434.4 (428.80)	2464.3 (463.91)
	Median	621.5	582.3	1076.4	2319.6	2292.8
	Min, Max	291, 700	495, 942	854, 1640	1942, 3096	2142, 3130
T _{max} (h)	N	4	5	5	5	4
	Median	1.0	1.0	1.0	1.0	1.0
	Min, Max	1, 2	1, 1	1, 1	1, 2	1, 1
AUC _{0-last} (h*ng/mL)	N	4	5	5	5	4
	Mean (SD)	6671.4 (2006.87)	10332.1 (4912.06)	18043.4 (7908.47)	37015.0 (7920.00)	37537.9 (4543.67)
	Median	6811.0	8177.8	19620.0	36847.8	39221.7

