9.3. PHARMACODYNAMICS PARAMETERS

The following PD parameters will be calculated based on actual measurements of PD uric acid for each Cohort and Treatment period and Overall where possible:

C_{min}	Minimal observed serum concentration
T_{min}	Time of minimal observed serum concentration
CFB_{min}	Minimum observed change from baseline in serum concentration
$AUE_{CFBlast}$	Absolute value for Area under the change from baseline in effect-time curve from time zero to the time of the last quantifiable concentration (effect - uric concentration)
$TA_{AUE_{CFBlast}}$	Time adjusted area under the absolute value for effect-time curve from time zero to the time of last quantifiable concentration (effect - uric concentration)
T_{onset}	Time of onset of effect - first time point of reduction uric acid concentration >10% of baseline
$T_{resolve}$	Time of resolution of effect - first time point of return of uric acid concentration to baseline defined as <10% difference from pre-dose baseline
$T_{duration}$	Time of duration of effect, calculated as $T_{resolve} - T_{onset}$

The following PD parameters will be calculated based on %CFB of PD uric acid for each Cohort and Treatment period and Overall where possible

Statistical Analysis Plan

$\%CFB_{\min}$	Minimum %CFB in serum concentration
$AUE_{\%CFB_{\text{last}}}$	Absolute value for Area under the %CFB in effect-time curve from time zero to the time of the last quantifiable concentration (effect - uric concentration)
$TA_AUE_{\%CFB_{\text{last}}}$	Time adjusted area under the %CFB for effect-time curve from time zero to the time of last quantifiable concentration (effect - uric concentration)
# and % of patients with $SUA < 6$ in TP3	The number and % of patients maintaining sUA concentrations below 6 mg/dL at the end of treatment period 3
# and % of patients with $SUA < 6$ in TP5	The number and % of patients maintaining sUA concentrations below 6 mg/dL at the end of treatment period 5

9.3.1. Handling of Dropouts, Missing Data or Data Below the Lower Limit of Quantification

Missing concentration data for all subjects who are administered scheduled study treatments will be considered as non-informative missing and will not be imputed. No concentration estimates will be provided for missing sample values.

For the derivation of PD parameters, serum concentration summary, individual serum concentration versus time curves and mean concentration versus time graphs the following rules will apply:

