- Concentration values below the assay's lower limit of quantification (BLQ) for all time points will be treated as zero
- The sampling time of pre-dose samples relative to dosing will also be treated as zero
- If the actual time of sampling is missing, the planned time may be used
- In case of discrepancy between the nominal time and time stamp on the sample concentration data, which affects the temporal order of PD samples and is not related to documented protocol deviations, the nominal (planned) time will be used only for the pre-dose samples before treatment period 1. All other data with such time discrepancy will be removed from PD parameter derivations and summaries. The profiles for subjects with the single PD points removed due to this type of discrepancy can still be used for derivation of PD parameters and any summaries or models for other PD time points.

Statistical Analysis Plan

Samples taken outside the sampling windows may be excluded from by-time point summary statistics. This will be determined prior to the start of analyses around database lock.

No further imputation will be applied to any missing values.

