Mean time response profiles for uric acid concentration raw values and %CFB at each time point for each Treatment period and cohort plotted against time for each Cohort separately with curves for all Treatment periods overlaid on one plot. BLQ values for uric acid concentration will be assigned 0 values for linear scales and 1/10 of LLOQ values for all time points for the graphic representation on log-linear scales only. Actual measured concentrations will be presented on both linear and log-linear scales while %CFB profiles will be presented on linear scale only.

Box plots for each derived PD parameter based on actual measurements and %CFB: CFB_{min}, AUE_{CFBlast}, TA_AUE_{CFBlast} will also be plotted by treatment.

Individual profiles for uric acid concentration absolute values and %CFB will be plotted for each Treatment period and cohort on a separate plot.

9.7. ASSESSMENT OF THE EFFECTS OF SEL-110 (RAPAMYCIN) AND SEL-037 (PEGSITICASE) ON PD PARAMETERS OF URIC ACID

Assessments done outside the assessment windows may be excluded from summarization. This will be determined prior to database lock.

The key PD parameters based on measured values and %CFB %CFB_{min}, AUE_{%CFBlast}, and TA_AUE_{%CFBlast} as well as uric acid concentration and %CFB on day 21 of each treatment period will be analyzed using linear mixed model for the response to SEL-110 dose levels co-administered with either 0.2 or 0.4 mg/kg of SEL-037 (the dose level of SEL-110 for Cohorts 1 and 2 will be assigned as 0). Additionally contribution of SEL-110 to the PD effect of SEL-037 will be tested to compare the following (test - reference). For PD

Statistical Analysis Plan

parameters based on actual measured values baseline concentration of uric acid will be incorporated in the model as covariate.

For Parts A and B following contrasts will be tested:

Cohort 3 Part A vs Cohort 1 Part A
Cohort 5 Part A vs Cohort 1 Part A
Cohort 7 Part A vs Cohort 1 Part A
Cohort 4 Part A vs Cohort 2 Part A
Cohort 6 Part A vs Cohort 2 Part A
Cohort 8 Part A vs Cohort 2 Part A
Cohort 10 Part A vs Cohort 2 Part A
Cohort 12 Part A vs Cohort 2 Part A
Cohort 1 Part A vs Cohort 2 Part A
Cohort 3 Part A vs Part B
Cohort 5 Part A vs Part B
Cohort 7 Part A vs Part B
Cohort 4 Part A vs Part B
Cohort 6 Part A vs Part B
Cohort 8 Part A vs Part B
Cohort 10 Part A vs Part B
Cohort 12 Part A vs Part B

For Part C (cohorts 13, 15, 17) additional contrasts will be:

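### The uric acid area endpoints end at the last quantifiable value, so, read literally, a subject who stays below quantification loses nearly all of the un-adjusted area

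*SAP*

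**What the plan says.** SAP 4.2 and 9.3 define AUE_CFBlast as the absolute area under the change-from-baseline curve "from time zero to the time of the last quantifiable concentration (effect - uric concentration". SAP 9.3 gives the percent-change version the same limit. The time-adjusted form is the "Time adjusted area under the absolute value for effect-time curve from time zero to the time of last quantifiable concentration"; its divisor is not stated.

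SAP 9.3.1 governs values below quantification. It applies "For the derivation of PD parameters, serum concentration summary, individual serum concentration versus time curves and mean concentration versus time graphs", and its rule is: "Concentration values below the assay's lower limit of quantification (BLQ) for all time points will be treated as zero". It says nothing about where the area ends.

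Protocol 4.3.2.1 reports that, after a single dose of SEL-037, uric acid was "below quantification limits from Study Day 2 for all subjects (N=22"). Protocol 4.3.2.3 reports for the combination: "The uric acid level of all subjects treated with SEL-212 dropped to below 0.1 mg/dL within 24 hours after infusion".

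SAP 9.7 names %CFBmin and the percent-change AUE and TA_AUE as key PD parameters. These, "as well as uric acid concentration and %CFB on day 21 of each treatment period will be analyzed using linear mixed model", with cohort contrasts; the example code takes the logarithm of the parameter. SAP 9.4 also summarises the areas by geometric mean.

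**The concern.** Ending an area at the last quantifiable value suits a drug concentration that decays to nothing, because little is lost after that point. Uric acid under a uricase runs the other way: the effect is greatest when the analyte cannot be measured. If the limit is applied as written, the area stops just as full effect is reached and restarts only if control is lost.

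The AUE family feeds the SEL-110 dose-response model and contrasts in SAP 9.7, the PK-PD correlations in the same section, and the tables in SAP 10.4 and 10.5 that compare antibody-positive with antibody-negative subjects. Sustained control and absence of antibodies are what SEL-110 is meant to produce. An area that shrinks with sustained control would blur or reverse that comparison for the affected parameters.

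**Working it through.** The documents give no figure for these areas, so there is nothing to reproduce. The check is an illustration of the stated rule.

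**Inputs**
- Period 1 times from the start of SEL-037 (SAP 9.2, Cohorts 1-2): pre-dose set to 0, then 0.5, 1, 2, 5, 8, 23, 167, 335, 503 and 671 h.
- BLQ = 0 (SAP 9.3.1).
- Baseline 8 mg/dL: assumed. Entry requires at least 6 at screening (SAP 3.5.1).
- Initial fall, the same for everyone: 8, 6.5, 5, 3, 1 mg/dL at 0, 0.5, 1, 2, 5 h, then BLQ from 8 h. Assumed. The quantification limit is not given.
- TA_AUE = area / elapsed time to the end of the area. Assumed.

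**Formula.** With d = 8 − uric acid, area = Σ (t₂ − t₁)(d₁ + d₂)/2. The values of d at 0, 0.5, 1, 2, 5 and 8 h are 0, 1.5, 3, 5, 7 and 8.

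**Full responder, literal limit (5 h).** 0.375 + 1.125 + 4 + 18 = 23.5. TA = 23.5/5 = 4.7.

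**Full responder, whole interval.** Adding 5-8 h: 3 × 7.5 = 22.5, giving 46. Adding 8-671 h: 663 × 8 = 5,304. Total 5,350; TA = 5,350/671 = 8.0.

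**Response lost by Day 14** (6 mg/dL at 335 h, 8 at 503 and 671 h). 46 + 159 × 8 + 168 × (8 + 2)/2 + 168 × (2 + 0)/2 = 46 + 1,272 + 840 + 168 = 2,326. TA = 2,326/671 = 3.5.

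**Response lost by Day 21** (BLQ to 335 h, 8 at 503 and 671 h). 46 + 327 × 8 + 168 × (8 + 0)/2 = 46 + 2,616 + 672 = 3,334. TA = 3,334/671 = 5.0.

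| Subject | AUE, literal (mg·h/dL) | AUE, whole interval | TA_AUE, literal (mg/dL) | TA_AUE, whole interval |
|---|---|---|---|---|
| BLQ to Day 28 | 23.5 | 5,350 | 4.7 | 8.0 |
| Lost by Day 14 | 2,326 | 2,326 | 3.5 | 3.5 |
| Lost by Day 21 | 3,334 | 3,334 | 5.0 | 5.0 |

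Un-adjusted AUE is reversed by a factor of about 100 (2,326/23.5 = 99). The percent-change area multiplies every row by 100/8 = 12.5, so its order is the same. TA_AUE is understated for the responder; its order is right against loss by Day 14 and wrong against loss by Day 21.

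**Other profiles.** A second set used the Cohort 3-12 times from first infusion, baseline 8 and an assumed quantification limit of 0.1 mg/dL.
- Un-adjusted area, literal limit: full responders last quantifiable at 2, 9 or 24 h get 3.2, 40.5 and 151.5. Subjects losing response by Day 7, 14 or 21 get 879, 2,137 and 3,481. Every responder is below every loser, and the order is the same at baselines 6 and 10.
- TA_AUE, literal limit: responders 1.6, 4.5 and 6.3; losers 1.3, 3.2 and 5.2. The order is mixed.
- One value of 0.2 mg/dL at Day 28 in an otherwise BLQ profile gives 5,346, because the area then spans the whole period.

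**Later periods.** Under Protocol 6.3.1, SEL-110 cohorts continue only if Day 21 uric acid is at most 1.0 mg/dL, so Periods 2-5 are enriched for deep responders. A subject BLQ at every sample, pre-dose included, has no last quantifiable time. The area is undefined and cannot enter a log-scale model or a geometric mean.

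**Check of the fix.** With the limit at the last sample and BLQ as zero, the second set gives responders 5,312 to 5,376 and TA 7.9 to 8.0, above every loser on both measures. The order also holds at baselines 6 and 10.

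**The case against.** The strongest reply is that SAP 9.3.1 already settles the matter. It is written for PD parameter derivation and makes BLQ samples zeros at all times, whereas the PK rule in SAP 8.2.1 sets later BLQ values to missing. If those zeros count as values up to the last sample, nothing is lost. That reading is possible, but the SAP does not state it. Two places favour the literal reading: SAP 8.2 ties the end of the PK area to the last measurable concentration, and SAP 9.4 still counts samples as BLQ although they are summarised as zero.

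The reply is right on three other points. Only subjects still BLQ at the end of the period are affected. The Phase 1 passages show early loss of quantification, not four weeks of it as the norm: Protocol 4.3.2.1 describes two subjects at Day 30 as below 1, not as unquantifiable. And the consequences are limited: the primary objective is safety, the PK-PD correlations are exploratory, and SAP 10.5 makes no inference in its antibody comparisons.

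A reader might infer that dividing by time leaves the ranking reversed as well. The figures do not support that as a general statement: 4.7 against 3.5 keeps the correct order, while 4.7 against 5.0 does not.

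**Conclusion.** The concern holds as a conflict between a stated integration limit and a BLQ rule that does not override it. Applied literally, the limit misranks un-adjusted AUE and its percent version for subjects still BLQ at the end of a period (23.5 against 2,326, where 5,350 is the full value). It understates their TA_AUE (4.7 instead of 8.0), with the ranking depending on the profile. It leaves a subject who is BLQ throughout a later period with no area.

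A reader might go further and infer that the trial's PD conclusions would be reversed. The documents do not support that. %CFBmin, Day 21 uric acid and its percent change, and the counts below 6 mg/dL do not use this limit and would still show sustained control.

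The sizes rest on an assumed baseline, assumed profiles, an unstated quantification limit and an assumed time divisor. How many subjects are affected cannot be known from the documents. This is a should-fix for secondary PD parameters.

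**What to change.** In SAP 4.2 and 9.3, define AUE and TA_AUE, on both the actual and the percent scale, from time zero to the last uric acid sample collected in the treatment period: the next pre-dose sample, or the end-of-study or final sample. State that BLQ samples count as observed zeros under 9.3.1 and that TA_AUE is the area divided by that sampled time.

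The cost is about one sentence in each section and a changed setting in the parameter derivation. No new data are needed. It should be settled before database lock, so that the choice of reading is not made with the results in view.

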1. GLOSSARY OF ABBREVIATIONS

Abbreviation	Description
ADA	Anti-drug antibody
AE	Adverse event
aPTT	Activated partial thromboplastin time
AST	Aspartate aminotransferase
AUCinf	Serum concentration-time curve from time 0 to infinity
AUClast	Serum concentration-time curve from time 0 to the time of last quantifiable concentration
CBC	Complete blood count
CL	Serum clearance of drug
Cmax	Maximum observed serum concentration
CRF	Case report form
CRO	Contract research organization
D	Day, Study day
dL	Deciliter
DLT	Dose-limiting toxicity
ECG	Electrocardiogram
FAAN	Food Allergy & Anaphylaxis Network
FDA	US Food and Drug Administration
GCP	Good Clinical Practice
H	Hour
HED	Human equivalent dose
HIV	Human immunodeficiency virus
ICF	Informed consent form
ICH	International Conference on Harmonization
IEC	Independent Ethics Committee
IND	Investigational New Drug
INR	International normalized ratio
IRB	Institutional Review Board
Kel	Terminal elimination rate constant
kg	Kilograms
LLOQ	Lower limit of quantification
MedDRA	Medical Dictionary for Regulatory Activities
mg	Milligrams
ml	Milliliters
MTD	Maximum tolerated dose
NIAID	National Institute of Allergy and Infectious Diseases
PD	Pharmacodynamic
PEG	Polyethylene glycol

1008142

SELECTA Biosciences

SEL - 212/201

SAP Version: Final 2.0

Statistical Analysis Plan

Abbreviation	Description
PK	Pharmacokinetic
PTT	Partial thromboplastin time
SAE	Serious adverse event
SAP	Statistical Analysis Plan
SEM	Standard error of the mean
t _{1/2}	Terminal half-life
TEAE	Treatment-emergent adverse events
T _{max}	Time at which C _{max} occurred
ULN	Upper limit of normal
USP	United States Pharmacopeia
V	Visit
V _{ss}	Apparent volume of distribution at equilibrium
V _d	terminal volume of distribution
C _{max} /C _{min}	Maximum/minimal observed serum concentration
T _{max} /T _{min}	Time of maximum/minimal observed serum concentration
CFB _{max} , CFB _{min}	Maximum/minimum observed change from baseline in serum concentration
T _{CFBmax} , T _{CFBmin}	Time of maximum/minimal observed change from baseline in serum concentration
AUE _{CFBlast}	Area under the change from baseline in effect-time curve from time zero to the time of the last quantifiable concentration (effect - uric concentration)
TA_AUE _{CFBlast}	Time adjusted area under the effect-time curve from time zero to the time of last quantifiable concentration (effect - uric concentration)

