4.2. PHARMACODYNAMIC ENDPOINTS

The following PD parameters will be calculated on PD uric acid for each Cohort and Treatment period and Overall where possible. The parameters will be derived for actual measurements of uric acid as well as for % change from baseline:

C_{min}	Minimal observed serum concentration
T_{min}	Time of minimal observed serum concentration
CFB_{min}	Minimum observed change from baseline in serum concentration
$AUE_{CFBlast}$	Absolute value for Area under the change from baseline in effect-time curve from time zero to the time of the last quantifiable concentration (effect - uric concentration)
$TA_{AUE_{CFBlast}}$	Time adjusted area under the absolute value for effect-time curve from time zero to the time of last quantifiable concentration (effect - uric concentration)
T_{onset}	Time of onset of effect - first time point of reduction uric acid concentration >10% of baseline
$T_{resolve}$	Time of resolution of effect - first time point of return of uric acid concentration to baseline defined as <10% difference from pre-dose baseline
$T_{duration}$	Time of duration of effect, calculated as $T_{resolve} - T_{onset}$

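### The SAP defines the four uric acid area parameters in three incompatible ways, and the wording of TA_AUE_CFBlast counts uric acid above baseline as drug effect

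*SAP*

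**What the plan says.** SAP 9.3 lists four uric acid area parameters.

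- AUE_CFBlast: "Absolute value for Area under the change from baseline in effect-time curve from time zero". The modulus is applied to the area.
- AUE_%CFBlast: "Absolute value for Area under the %CFB in effect-time curve from time zero". The same form on the percent scale.
- TA_AUE_CFBlast: "Time adjusted area under the absolute value for effect-time curve from time zero to the time of last quantifiable concentration". The modulus is applied to the curve, which is then integrated.
- TA_AUE_%CFBlast: "Time adjusted area under the %CFB for effect-time curve from time zero". No absolute value.

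SAP 4.2 words the two measured-scale parameters as in 9.3 ("Absolute value for Area under the change from baseline in effect-time curve" and "Time adjusted area under the absolute value for effect-time curve") and says the parameters are also derived for percent change. The SAP glossary gives TA_AUE_CFBlast as "Time adjusted area under the effect-time curve from time zero to the time of last quantifiable concentration", and it defines AUE_CFBlast without an absolute value too.

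Baseline is one pre-dose value from Period 1 (SAP 6.2). Percent change is signed, so a reduction is negative (SAP 9.1). SAP 9.4 asks for geometric means and geometric CVs of all four areas, and the example code in 9.7 models the natural log of the PD parameter. No section says how time above baseline is to be treated.

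**The concern.** These parameters are meant to measure uric acid reduction, so a period above baseline should lower the score or at least not raise it. If the modulus is taken before integration, it raises the score.

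Relapse is expected in this trial. With single doses of SEL-037 alone, Protocol 4.3.2.1 reports that the effect lasted to Day 7 in all but one of 22 subjects and to Day 30 in one. A relapsed subject does not need a true rebound to be affected. Ordinary variation around a single baseline value puts some readings above it.

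TA_AUE_CFBlast feeds the summaries (9.4), the box plots (9.6), the PK-PD correlations (9.7) and the descriptive comparisons by antibody status (10.4 and 10.5). In each, relapsed subjects would look closer to sustained responders than they are. Separately, two programmers working from 4.2, 9.3 and the glossary could derive different numbers for the same parameter.

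**Working it through.** The documents give no figure for these endpoints, so there is nothing to reproduce. The check applies each definition to assumed profiles.

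**Inputs.** Sampling at 0, 0.5, 1, 2, 5, 8, 23, 167, 335, 503 and 671 h from the start of SEL-037 (SAP 9.2, Periods 1-3). Baseline 8 mg/dL is an assumption; the documents give only the entry floor of 6. Uric acid is assumed to be 8, 4, 2, 0.5, 0, 0, 0 at the first seven times. Integration is by linear trapezoid with exact baseline crossings. The time-adjusted value is area / 671 h.

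**Common part, 0-23 h.** Area below baseline = 1 + 2.5 + 6.75 + 23.25 + 144 = 177.5 mg·h/dL.

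**Profiles on which the definitions agree in size.**
- Sustained response: 177.5 + 8 × 648 = 5361.5; time-adjusted 7.99.
- Control at day 7, exactly at baseline from day 14: 177.5 + 8 × 144 + 8 × 168/2 = 2001.5; time-adjusted 2.98.
- Exactly at baseline from day 7: 177.5 + 8 × 144/2 = 753.5.

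**Relapse seen at day 14, settling above baseline.**
- At +10% (0.8 mg/dL): area below = 177.5 + 1152 + 610.9 = 1940.4; area above = 6.1 + 268.8 = 274.9. Modulus first: 2215.3, or 3.30 mg/dL. Signed: 1665.5, or 2.48. Excess 33% (14% against the below-baseline area alone, 2.89).
- At +25% (2 mg/dL): below = 1867.1; above = 705.6. Modulus first: 2572.7, or 3.83. Signed: 1161.5, or 1.73. Excess 122% (38% against the below-baseline area alone).

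As the relapse goes from baseline to +10% to +25%, TA_AUE_CFBlast as worded rises 2.98, 3.30, 3.83. AUE_CFBlast as worded falls 2001.5, 1665.5, 1161.5.

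**When the modulus after integration fails.** For relapse seen at day 7 to +25%, change from baseline has a signed area of +398.5, a net worsening. AUE_CFBlast reports it as 398.5 of effect. Uric acid 10% above baseline throughout is reported as 536.6.

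**Scatter around baseline, no rebound.** Let relapsed values be independent Normal around baseline with standard deviation SD. Between two such values *a* and *e*, the mean height of |curve| is (|a|+|e|)/2 if the signs agree (expectation 0.798 SD) and (a²+e²)/(2(|a|+|e|)) if they differ (expectation 0.497 SD). The average is about 0.648 SD; the signed mean is zero.
- Day 14: two 168 h segments, 336 × 0.648 = 218 × SD. At SD 1, 218/2001.5 = 10.9%; at SD 0.5, 5.4%.
- Day 7: three segments, 504 × 0.648 = 327 × SD. At SD 1, 327/753.5 = 43%; at SD 0.5, 21.7%.

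The segment in which uric acid climbs back adds, at SD 1, at most (0.5/8) × 168 = 10.5 for day 14 (0.5 points) and (0.5/8) × 144 = 9 for day 7 (1.2 points). Rounded, that is about 6% to 11% and about 21% to 43%.

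**TA_AUE_%CFBlast.** It is signed, so every reduction gives a negative number. Neither its logarithm nor its geometric mean exists.

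**The case against.** The strongest defence is that absolute in the TA_AUE_CFBlast row means raw scale, in contrast to percent. SAP 9.6 uses the word that way: "Individual profiles for uric acid concentration absolute values and %CFB will be plotted". The glossary, with no absolute value, points the same way. This leaves the wording ambiguous but does not clear it. In the 9.3 table the same term also sits on the AUE_%CFBlast row, where it cannot mean non-percent, so modulus is the more natural reading there.

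A reader might infer that all four area endpoints count a rise as effect. The documents do not support that. For the two AUE rows a rise subtracts while the net is still a reduction, and TA_AUE_%CFBlast has no modulus.

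A reader might also infer that the 9.7 contrasts between SEL-110 cohorts and SEL-037 alone are diluted. The area parameters named for that model are AUE_%CFBlast and TA_AUE_%CFBlast. The reference there to measured values, with a baseline covariate for them, leaves room for the raw forms, but TA_AUE_CFBlast is not named.

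A quick continuous-time calculation gives larger figures: full control for 7 days and then 21 days at SD 1 gives 0.798 × 21 = 16.8 on 56 mg·d/dL, or 30%. That assumes instant relapse and continuous observation, and the SAP samples weekly after Day 1.

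Exposure is limited as well. The Day 21 rule in Protocol 6.3.1 largely confines relapse in the SEL-110 cohorts to a subject's last dosed period, though that period stays in the analysis. The antibody comparisons in 10.5 carry no inference.

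**Conclusion.** The definitions conflict and should be corrected before the derivations are programmed. One parameter, TA_AUE_CFBlast, rewards uric acid above baseline as literally worded. The two AUE parameters lose the sign only when the whole-period net is above baseline, where net worsening becomes positive effect. TA_AUE_%CFBlast cannot enter the planned log model or geometric mean.

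The sizes shown apply to TA_AUE_CFBlast alone. They rest on an assumed baseline, assumed scatter and assumed relapse times; the documents give no rebound data.

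These are secondary pharmacodynamic measures in a trial whose primary objective is safety. The tables of subjects below 6 mg/dL and the Day 21 uric acid analyses are not affected.

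**What to change.** In the glossary, 4.2 and 9.3, define all four parameters as the signed area of (baseline minus uric acid), positive for a reduction and negative for a rise. Use one rule for the measured and percent forms, with no modulus before or after integration.

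Signed values can be zero or negative, so the downstream analyses must change too. In 9.7, analyse these area parameters on the original scale and report differences in means with confidence intervals. In 9.4, drop the geometric mean and geometric CV for them. Without this step, a log analysis would fail on, or drop, the subjects with the worst relapse.

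The cost is SAP wording and derivation code, with no burden on sites. The downside is that geometric mean ratios, and so the 80-125% criterion, are no longer available for these parameters.
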